4.6 Changes to Analysis from Protocol

Per protocol, the variable “reason for VKA switch will be described under the OAC treatment management outcome. Finally, reason for VKA treatment switch has not been collected specifically in the VKA section of the CRF. This has been deleted from section 14.2.2 of SAP.

New analysis not included in the final protocol have been considered:

- Antiplatelet treatment according to current NOAC type
- Treatment received at the moment of thromboembolic and bleeding events.
- For all NOACs, the different doses that patients take according to HAS-BLED score.
- Underdosed and overdosed patients (for current NOAC treatment).
- HAS-BLED total score according to NOAC and antiplatelet current treatment.
- Multivariate model to evaluate the association between the Clinical Frailty Scale (dependent variable) and the thromboembolic and the bleeding events (independent variables). To calculate this analysis, only events that have occurred subsequent to the start of anticoagulant therapy (not those prior to the start of VKA / NOACs) will be considered. Univariate analysis will be performed. All variables which have a P value of less than 0.1 will be included in the multivariate analysis.

Document:	H:\HOR-Europe\2019\2512352 - Study on anticoagulation management - BI\Proyecto\Estadistica\SAP\S		
	AP_REBELD_version1.0_08072020.docx		
Author:	██████████	Version Number:	Version 1.0
		Version Date:	[08072020]

Template No.: RWI_TP_BIOS0013 Revision 1

Reference: RWI_WI_BIOS0015

Effective Date: 15Jun2018

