7.2.3 Charlson Comorbidity Index

The Charlson Comorbidity Index (CCI) predicts the ten-year mortality for patients presenting one or more of the conditions in the model, where the age groups and each condition are awarded a specific number of points, some conditions weighing more than others, based on the adjusted risk of mortality. The more points given, the more likely the predicted adverse outcome. The index then sums the points and offers a 10-year survival/ mortality prognosis.

[https://www.thecalculator.co/health/Charlson-Comorbidity-Index-\(CCI\)-Calculator-765.html](https://www.thecalculator.co/health/Charlson-Comorbidity-Index-(CCI)-Calculator-765.html)

<https://www.mdcalc.com/charlson-comorbidity-index-cci>

Document:	H:\HOR-Europe\2019\2512352 - Study on anticoagulation management - BI\Proyecto\Estadistica\SAP\S		
	AP_REBELD_version1.0_08072020.docx		
Author:	██████████	Version Number:	Version 1.0
		Version Date:	[08072020]

Template No.: RWI_TP_BIOS0013 Revision 1

Reference: RWI_WI_BIOS0015

Effective Date: 15Jun2018

Each of the conditions listed below are awarded 1, 2, 3 or 6 points depending on the mortality risk. CCI will be calculated as the sum of all points included in the following table:

Table 2. Point assigned to Charlson Comorbidity Index

	POINTS
Age	
50–59 years	+1
60–69 years	+2
70–79 years	+3
>=80 years	+4
Myocardial infarction	+1
Congestive Heart Failure (CHF)	+1
Peripheral vascular disease	+1
Cerebrovascular Accident or Transient ischemic attack	+1
COPD	+1
Connective tissue disease	+1
Peptic ulcer disease	+1
Liver disease	
Mild	+1
Moderate to severe	+3
Diabetes mellitus	
Uncomplicated	+1
End-organ damage	+2
Hemiplegia	+2
Moderate to severe* Chronic Kidney Disease (CKD)	+2
Solid tumor	
Localized	+2
Metastatic	+6
Leukemia	+2
Lymphoma	+2
AIDS	+6

Document: H:\HOR-Europe\2019\2512352 - Study on anticoagulation management - BI\Proyecto\Estadística\SAP\SAP_REBELD_version1.0_08072020.docx

Author: [REDACTED] Version Number: Version 1.0
Version Date: [08072020]

Template No.: RWI_TP_BIOS0013 Revision 1

Reference: RWI_WI_BIOS0015

Effective Date: 15Jun2018

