Comorbidities and Clinical Risk Factors: - Heart Failure (Yes/No, New York Heart Association (NYHA) classification; Left Ventricular Ejection Fraction, LVEF, %) - Coronary artery disease (Yes/No) - Sleep apnoea-hypopnoea syndrome (SAHS) (Yes/No) - Hypertension (Yes/No) -Hyperlipidemia (Yes/No) - Comorbidity Charlson index (Yes/No; total score): myocardial infarction (already collected for history of thromboembolic events), congestive heart failure (already collected for the NYHA scale scoring), cerebral and peripheral vascular disease, dementia, chronic obstructive pulmonary disease, connective tissue disease, peptic ulcer disease, mild/moderate/severe liver disease, diabetes, diabetes with end-organ damage, hemiplegia, moderate/severe renal disease, any solid tumor, metastatic solid tumor, leukemia, lymphoma AIDs, age (already collected as a demographic characteristic). -History of thromboembolic events (Yes/No, number and date): TIA, ischemic stroke, hemorrhagic stroke, embolism systemic, deep vein thrombosis, pulmonary embolism, stable angina, unstable angina, myocardial infarction with/without ST segment elevation; and bleeding events (Yes/No, number and date): intracranial, digestive, genitourinary, gingival, nasal, pulmonary, articular-muscular, conjunctival.	x	x (NYHA classification, Charlson Index)
CHA2DS2-VASc (total score)		x
HAS-BLED (total score)		x
Clinical Frailty Scale		x
Previous vitamin K antagonist (VKA) treatment (yes/no), type (acenocoumarol or warfarin), start date and treatment duration		
Other concomitant treatments (Total number of current concomitant drugs; Type (Yes/No, number): ARB or ACE inhibitor, Beta-blocker, Calcium channel blockers, Diuretics, Amiodarone, Statin, Proton pump inhibitor, H2-receptor antagonist, Digoxin, NSAIDs, Dronedarone, Other antiarrhythmics, ketoconazole (systemic), cyclosporine, itraconazole	x	

Document: H:\HOR-Europe\2019\2512352 - Study on anticoagulation management - BI\Proyecto\Estadística\SAP\S AP_REBELD_version1.0_08072020.docx

Author: [REDACTED] Version Number: Version 1.0
Version Date: [08072020]

Template No.: RWI_TP_BIOS0013 Revision 1

Reference: RWI_WI_BIOS0015

Effective Date: 15Jun2018

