14.6 Exploratory analysis

History and current antiplatelet treatment will be described by current NOAC type.

Treatment received at the time of thromboembolic and bleeding events will be described, including NOAC, VKA and antiplatelet treatments.

Doses of current NOAC treatment received by the patient will be described according to HAS-BLED score (as low, intermediate and high risk).

The percentage of underdosed and overdosed patients for current NOAC treatment will be described.

HAS-BLED total score (as <3 , $3-5$, ≥ 5) will be described according to NOAC and antiplatelet current treatment.

Multivariate logistic regression will be used to evaluate the association between the Clinical Frailty Scale (dependent variable: Frailty patients - CFS scoring >4 vs Non-frailty patients - CFS scoring ≤ 4) and the thromboembolic and the bleeding events (independent variables). To calculate this analysis, only events that have occurred subsequent to the start of anticoagulant therapy (not those prior to the start of VKA / NOACs) will be considered. Other factors will be age, sex, BMI, smoking habit, alcohol consumption, time since NVAf diagnosis, NVAf type, modified EHRA scale, procedures and interventions, comorbidity Charlson index and clinical risk factors. Univariate analysis will be performed. All variables which have a P value of less than 0.1 will be included in the multivariate analysis.

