	Apixaban (Serum creatinine $< 1,5$ mg/dl or creatinine clearance ≥ 30 mL/min)			NA
	Apixaban (Serum creatinine $\geq 1,5$ mg/dl or creatinine clearance < 30 mL/min)		NA	
Edoxaban	Edoxaban (Body weight > 60 kg)			NA
	Edoxaban (Body weight ≤ 60 kg)		NA	
	Edoxaban (creatinine clearance > 50 mL/min)			NA
	Edoxaban (creatinine clearance 15-50 mL/min)		NA	

Table 52. HAS-BLED score according NOAC+antiplatelet current treatment

		HAS-BLED score				
		Valid N	< 3	3-5	≥ 5	N missing
Current treatment	Dabigatran+aspirin					
	Dabigatran+clopidogrel					
	Dabigatran+peasugrel					
	...					
	... (for all combinations)					

Row percentage will be calculated

Document: H:\HOR-Europe\2019\2512352 - Study on anticoagulation management - BI\Proyecto\Estadistica\SAP\S AP_REBELD_version1.0_08072020.docx

Author: [REDACTED]

Version Number:

Version 1.0

Version Date:

[08072020]

Template No.: RWI_TP_BIOS0013 Revision 1

Reference: RWI_WI_BIOS0015

Effective Date: 15Jun2018

Table 53. Multivariate logistic model to evaluate the association between the Clinical Frailty Scale and the thromboembolic and the bleeding events

Variable	Estimate	Standard error	t-value	Pr> t	OR

*dependent variable: CFS in two categories: Frailty patients - CFS scoring >4 vs Non-frailty patients - CFS scoring ≤4)

*independent variables: thromboembolic and bleeding events. Other factors will be age, sex, BMI, smoking habit, alcohol consumption, time since NVAF diagnosis, NVAF type, modified EHRA scale, procedures and interventions, comorbidity Charlson index and clinical risk factors. Univariate analysis will be performed and all variables which have a P value of less than 0.1 will be included in the multivariate analysis.

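### The exploratory frailty model in SAP 14.6 lets a p<0.1 screen remove the event terms it is meant to evaluate; separately, the Charlson points table shows no dementia row

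*SAP*

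**What the plan says.** **The model.** SAP 4.6 adds an analysis that is not in the protocol: "Multivariate model to evaluate the association between the Clinical Frailty Scale (dependent variable) and the thromboembolic and the bleeding events (independent variables"). SAP 14.6 specifies it as a logistic regression of CFS >4 versus ≤4. It counts "only events that have occurred subsequent to the start of anticoagulant therapy" and lists further candidate factors, including age, sex, NVAF type and the Charlson index. The entry rule is "All variables which have a P value of less than 0.1 will be included in the multivariate analysis". SAP 4.6 has the same rule, and the Table 53 footnote repeats it: "Univariate analysis will be performed and all variables which have a P value of less than 0.1 will be included in the multivariate analysis". None of the three places exempts the event terms. Table 53 has columns for estimate, standard error, t-value, p-value and OR, but none for a confidence interval. SAP 8.2 and 8.3 still rule out any statistical test and any modelling.

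**The Charlson score.** SAP 7.2.3 states "CCI will be calculated as the sum of all points included in the following table", meaning Table 2, which shows no dementia row. Protocol Table 3, SAP Table 3 and mock Tables 12 and 22 all list dementia as a Charlson item. SAP 7 says the final score is calculated automatically from the answer to each item in the eCRF.

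**Shared items.** Table 2 gives a point for "Cerebrovascular Accident or Transient ischemic attack" with no time limit. SAP Table 3 describes the Charlson infarction item as "myocardial infarction (already collected for history of thromboembolic events"), and its event list begins "History of thromboembolic events (Yes/No, number and date): TIA, ischemic stroke, hemorrhagic stroke".

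**The concern.** A univariate screen is a way of choosing adjustment variables. Applied to the exposures under study, it decides whether they are reported at all. If an event term misses p<0.1, the reader learns only that its univariate p-value was 0.1 or more and sees no estimate or interval. If it passes, it does so partly because its estimate happened to be large. The harm is selective reporting of the two associations named as the purpose of the analysis.

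The missing dementia row matters for another reason. The Charlson score is summarised by NOAC type and by duration since first NOAC, with a standardized difference for Pradaxa versus other NOACs (SAP 14.3.1). Two definitions of the score would make those secondary summaries ambiguous. It also bears on the frailty model, because the Clinical Frailty Scale text in Protocol Annex 3 ties the grade of frailty to the grade of dementia.

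**Working it through.** **1. Screen**

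The plan gives no figure for this model, so there is nothing to reproduce. Inputs:

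- n = 500, from SAP 4.2.
- Two-sided p<0.1, so |z| must exceed 1.645, from SAP 14.6.
- 30% frail overall, event prevalence e from 3% (a single event type) to 17% (any event), and true OR 1.5 or 2.0. These are assumptions. The SAP gives no rates and does not say how events are coded.

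Formulas, with p1 and p0 the frail proportions with and without an event, chosen to give the stated OR and 30% frail overall:

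- SE(log OR) = √[1/(n·e·p1(1−p1)) + 1/(n(1−e)·p0(1−p0))]
- μ = ln(OR)/SE
- P(dropped) = 1 − P(Z > 1.645 − μ) − P(Z < −1.645 − μ)

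Example, e = 17% and OR 1.5:

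- There are 85 patients with an event and 415 without; p1 = 0.374 and p0 = 0.285.
- SE = √(1/19.90 + 1/84.53) = 0.249, and μ = 0.405/0.249 = 1.63.
- P(dropped) = 1 − 0.493 − 0.0005 = 0.51.
- If kept in the true direction, mean z = 1.627 + φ(0.018)/0.493 = 2.44. The geometric-mean OR is exp(2.44 × 0.249), about 1.8.

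The kept ORs below come from 400,000 simulated 2×2 tables. Simulated drop rates agree with the formula to within 0.02.

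| Event prevalence | Dropped, OR 1.5 | Dropped, OR 2.0 | Mean kept univariate OR, true 1.5 | Mean kept univariate OR, true 2.0 |
|---|---|---|---|---|
| 3% | 81% | 63% | 3.24 | 3.50 |
| 10% | 63% | 26% | 2.05 | 2.30 |
| 17% | 51% | 12% | 1.83 | 2.12 |

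With 20% to 40% frail, the drop rates across 3–17% prevalence are 48–82% at OR 1.5 and 11–66% at OR 2.0. A term with no association is left out about 90% of the time by construction. Without the screen, an estimate of 1.5 at 17% prevalence has 95% CI exp(0.405 ± 1.96 × 0.249) = 0.92 to 2.44.

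**2. Dementia**

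Every other Charlson item listed in SAP Table 3 has a row in Table 2. Omitting an item lowers the mean score by prevalence × weight. If 5–20% of patients had dementia, the shift is 0.05–0.20 per unit of weight. A difference of 5–15 percentage points in dementia prevalence between Pradaxa and other NOACs, with an assumed score SD of 2, moves the standardized difference by 0.05/2 to 0.15/2, that is 0.025 to 0.075 per unit of weight. Prevalence, imbalance and SD are all assumptions.

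**3. Charlson overlap**

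A counted infarction, stroke or TIA can also add a Charlson point. Simulations with a true thromboembolic OR of 1.5 (600,000 patients per setting; all event shares and Charlson effects assumed) give opposite answers according to which Charlson score drives frailty:

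| Score assumed to drive frailty | OR adjusting for total Charlson | OR adjusting for pre-anticoagulation Charlson |
|---|---|---|
| Before anticoagulation | about 1.2–1.4 | about 1.5 |
| At the study visit | about 1.5 | about 1.6–1.9 |

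**The case against.** **On the screen.** In SAP 14.6 the rule follows the list of other factors, so it could be meant only for them. That ambiguity is real. SAP 4.6 weighs against it, though as a summary it is not conclusive: it states the same rule and names no independent variables other than the events. The Table 53 footnote has no exemption either. It is also fair that the highest drop rates need 3% prevalence, that a 95% CI can be derived from the estimate and standard error of any term that appears, and that an unscreened interval of 0.92 to 2.44 is itself inconclusive. None of this supplies an estimate for a term that is left out.

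**On dementia.** Table 2 was read from extracted text and may be incomplete. The eCRF calculation may already score dementia. Both caveats stand, which is why the request is to check and reconcile.

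**On the overlap.** A reader might infer that adjusting for Charlson pulls the thromboembolic OR toward 1 and leaves bleeding untouched. The documents do not support that. They do not say whether the intended adjuster is comorbidity before anticoagulation or at the visit, and the direction of any bias depends on the answer. CFS is graded at the visit, so the second reading is plausible. An intracranial bleed recorded as a hemorrhagic stroke could also score a Charlson point. Nor would time-restricting the score be clean: the cerebrovascular item has no stated date, and coronary disease and coronary interventions remain as overlapping candidate factors.

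**Conclusion.** The screening point holds. As written, SAP 14.6, 4.6 and the Table 53 footnote allow the event terms to be dropped from a model whose purpose is to evaluate them. Assuming n=500 and 30% frail, this happens about half the time at OR 1.5 and 12% of the time at OR 2.0 with 17% prevalence, and more often for rarer events. The inflation figures are for univariate ORs; inflation of the adjusted ORs in Table 53 was not computed. The drop rates are one minus power at a two-sided 0.10 level, so they measure selective reporting and should not be read as lost power. The consequence is confined to one exploratory table and touches no primary or secondary objective.

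The dementia mismatch also holds as a discrepancy between passages, subject to the source PDF. It reaches the secondary summaries of the Charlson score, but the documents do not show that the delivered score omits dementia.

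The shared Charlson items are a note only. Neither the direction nor the size of any bias can be settled from the documents.

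**What to change.** - **SAP 14.6, 4.6 and Table 53 footnote:** keep both event terms in the model whatever their univariate p-value, and state how they are coded. The screen may stay for the other factors. Add 95% CIs for the event ORs to Table 53.
- **SAP 8.2 and 8.3:** except this exploratory model from the statements that no test and no modelling will be done.
- **SAP 7.2.3, Table 2:** after checking the source PDF, reconcile the table with the item lists and the eCRF calculation, so that one Charlson score including dementia feeds Tables 12 and 22 and the standardized differences.
- **Optional:** a sensitivity analysis with infarction and cerebrovascular items restricted to history before anticoagulation, where dates allow. This is not a required correction.

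The required changes are a few lines of text and code and need no new data. The cost is slightly wider intervals in the frailty model, because the event terms stay in regardless.

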15. SAFETY

All outputs for safety analysis will be based on the Safety Analysis Set.

Document:	H:\HOR-Europe\2019\2512352 - Study on anticoagulation management - BI\Proyecto\Estadística\SAP\S		
	AP_REBELD_version1.0_08072020.docx		
Author:	██████████	Version Number:	Version 1.0
		Version Date:	[08072020]

Template No.: RWI_TP_BIOS0013 Revision 1

Reference: RWI_WI_BIOS0015

Effective Date: 15Jun2018

15.1 Adverse Drug Reactions

The percentage of patients experiencing Adverse Drug Reactions related with BI product Pradaxa®, will be presented. Number and percentage of patients reporting each type of ADRs (SOC and PT) will be reported. ADRs will be described according to type, duration (days), seriousness, reason for seriousness and outcome. Adverse Drug Reaction term (open string variable) will be coded using Medical Dictionary for Regulatory Activities (MedDRA) central coding dictionary, the latest version available.

15.2 Serious Adverse Drug Reactions

Serious Adverse Drug Reactions (SADRs) are those ADRs recorded as “Serious” on the Adverse Events page of the (e)CRF. A summary of SADRs by SOC and PT will be prepared.

The percentage of patients experiencing serious related drug reactions (SADRs) with Pradaxa® will be presented. Number and percentage of patients reporting each type of SADRs will be reported.

15.3 Deaths

If any subjects die during Pradaxa® treatment, recorded on the “results in death” or outcome of event” as “fatal” on the (e)CRF, the information will be presented in a summary table and a data listing.

Document:	H:\HOR-Europe\2019\2512352 - Study on anticoagulation management - BI\Proyecto\Estadistica\SAP\SAP_REBELD_version1.0_08072020.docx		
Author:	██████████	Version Number:	Version 1.0
		Version Date:	[08072020]

Template No.: RWI_TP_BIOS0013 Revision 1

Reference: RWI_WI_BIOS0015

Effective Date: 15Jun2018

17. APPENDIX 1. MOCK TABLES

17.1 Eligibility

Table 5. Eligibility criteria – Patients in the FAS

		Dabigatran	Rivaroxaban	Apixaban	Edoxaban	Total
Total enrolled patients						
Eligible patients	Eligible patients (FAS)					
	Non-Eligible patients					
Reasons for non-eligible patients	Inclusion criteria 1					
	Inclusion criteria 2					

Table 6. Main stratification variables

		Total
Total eligible (FAS)		
NOAC type at study visit	Total Dabigatran Rivaroxaban Apixaban Edoxaban	
Duration since the first NOAC initiation date until the study visit	≤4 months > 4 months	

Document: H:\HOR-Europe\2019\2512352 - Study on anticoagulation management - BI\Proyecto\Estadística\SAP\S
AP_REBELD_version1.0_08072020.docx

Author: [REDACTED] Version Number: Version 1.0
Version Date: [08072020]

Template No.: RWI_TP_BIOS0013 Revision 1

Reference: RWI_WI_BIOS0015

Effective Date: 15Jun2018

17.2 Patient's characteristics

Total column will include description of total eligible sample (FAS).

17.2.1 Patient's characteristics according to current NOAC type

Table 7. Socio-demographic variables and habits according to current NOAC type

		Dabigatran	Rivaroxaban	Apixaban	Edoxaban	Total	Standardized differences (Pradaxa® vs others)
Age	Valid N Mean (SD) Median (Q1-Q3) Min-Max N missing						
Age group	Valid N 75-79 years 80-84 years ≥85 years N missing						
Sex	Valid N Male, n (%) Female, n (%) N missing						
Weight (Kg)	Valid N Mean (SD) Median (Q1-Q3) Min-Max N missing						
Weight (Kg) cat	Valid N ≤60 kg, n (%) >60 kg, n (%) N missing						
Height (cm)	Valid N Mean (SD)						

Document: H:\HOR-Europe\2019\2512352 - Study on anticoagulation management - BI\Proyecto\Estadistica\SAP\S AP_REBELD_version1.0_08072020.docx

Author: [REDACTED] Version Number: Version 1.0
Version Date: [08072020]

Template No.: RWI_TP_BIOS0013 Revision 1

Reference: RWI_WI_BIOS0015

Effective Date: 15Jun2018

		Dabigatran	Rivaroxaban	Apixaban	Edoxaban	Total	Standardized differences (Pradaxa® vs others)
	Median (Q1-Q3) Min-Max N missing						
BMI (Kg/m2)	Valid N Mean (SD) Median (Q1-Q3) Min-Max N missing						
BMI cat	Valid N Underweight: BMI < 18.5 kg/m2 Normal weight: 18.5 kg/m2 <= BMI <= 25 kg/m2 Overweight: 25 kg/m2 < BMI <= 30 kg/m2 Obese: 30 kg/m2 < BMI <= 35 kg/m2 Severely Obese: BMI > 35 kg/m2 N missing						
Caregiver	Valid N No Yes N missing						
Place where patients is living	Valid N Home alone At home with partner/other family member/a friend Other's home (e.g. family member's) Nursing home N missing						
Smoking habit	Valid N Ex-smoker						

Document: H:\HOR-Europe\2019\2512352 - Study on anticoagulation management - BI\Proyecto\Estadistica\SAP\S AP_REBELD_version1.0_08072020.docx

Author: [REDACTED]

Version Number:

Version 1.0

Version Date:

[08072020]

Template No.: RWI_TP_BIOS0013 Revision 1

Reference: RWI_WI_BIOS0015

Effective Date: 15Jun2018

		Dabigatran	Rivaroxaban	Apixaban	Edoxaban	Total	Standardized differences (Pradaxa® vs others)
	Smoker Non-smoker N missing						
Alcohol consumption	Valid N Casual Habitual Abuse Dependence N missing						

Table 8. Analytical laboratory results from the last available blood sample analysis according to current NOAC type

		Dabigatran	Rivaroxaban	Apixaban	Edoxaban	Total	Standardized differences (Pradaxa® vs others)
Serum creatinine (mg/dl)	Valid N Mean (SD) Median (Q1-Q3) Min-Max N missing						
Serum creatinine Normal levels: 0.6-1.2 mg/dl in males 0.5-1.1 mg/dl in females	Valid N Normal levels High/low level N missing						
Creatinine clearance (ml/min)	Valid N Mean (SD) Median (Q1-Q3) Min-Max N missing						
Creatinine clearance (ml/min): Cockcroft and Gault formula	Valid N Mean (SD) Median (Q1-Q3)						

Document: H:\HOR-Europe\2019\2512352 - Study on anticoagulation management - BI\Proyecto\Estadística\SAP\S AP_REBELD_version1.0_08072020.docx

Author: [REDACTED] Version Number: Version 1.0
Version Date: [08072020]

Template No.: RWI_TP_BIOS0013 Revision 1

Reference: RWI_WI_BIOS0015

Effective Date: 15Jun2018

		Dabigatran	Rivaroxaban	Apixaban	Edoxaban	Total	Standardized differences (Pradaxa® vs others)
	Min-Max N missing						
Creatinine clearance – range (ml/min/1.73m ²)	Valid N <15 15-29 30-59 60-89 ≥90 N missing						
AST (UI/L)	Valid N Mean (SD) Median (Q1-Q3) Min-Max N missing						
AST Normal values : 7-55 UI/L	Valid N Normal value High/low value N missing						
ALT (UI/L)	Valid N Mean (SD) Median (Q1-Q3) Min-Max N missing						
ALT Normal values: 8-48 UI/L	Valid N Normal value High/low value N missing						
Total bilirubin (mg/dl)	Valid N Mean (SD) Median (Q1-Q3) Min-Max N missing						
Total bilirubin Normal values: 0.2-1.2 mg/dl	Valid N Normal value High/low value						

Document: H:\HOR-Europe\2019\2512352 - Study on anticoagulation management - BI\Proyecto\Estadistica\SAP\S
AP_REBELD_version1.0_08072020.docx

Author: [REDACTED] Version Number: Version 1.0
Version Date: [08072020]

Template No.: RWI_TP_BIOS0013 Revision 1

Reference: RWI_WI_BIOS0015

Effective Date: 15Jun2018

		Dabigatran	Rivaroxaban	Apixaban	Edoxaban	Total	Standardized differences (Pradaxa® vs others)
	N missing						
Haemoglobin (g/dl)	Valid N Mean (SD) Median (Q1-Q3) Min-Max N missing						
Haemoglobin Normal values: 12-18 g/dl	Valid N Normal value High/low value N missing						
Platelet levels (x10 ³ /μL)	Valid N Mean (SD) Median (Q1-Q3) Min-Max N missing						
Platelet Normal values: 150 – 450 x10 ³ /μL	Valid N Normal value High/low value N missing						

Table 9. NVAf variables according to current NOAC type

		Dabigatran	Rivaroxaban	Apixaban	Edoxaban	Total	Standardized differences (Pradaxa® vs others)
Years since NVAf diagnosis	Valid N Mean (SD) Median (Q1-Q3) Min-Max N missing						
Years since NVAf diagnosis (patients treated previously with VKA)	Valid N Mean (SD) Median (Q1-Q3) Min-Max N missing						

Document: H:\HOR-Europe\2019\2512352 - Study on anticoagulation management - BI\Proyecto\Estadística\SAP\S AP_REBELD_version1.0_08072020.docx

Author: [REDACTED] Version Number: Version 1.0
Version Date: [08072020]

Template No.: RWI_TP_BIOS0013 Revision 1

Reference: RWI_WI_BIOS0015

Effective Date: 15Jun2018

		Dabigatran	Rivaroxaban	Apixaban	Edoxaban	Total	Standardized differences (Pradaxa® vs others)
Years since NVAF diagnosis (patients treated with NOAC as first anticoagulant)	Valid N Mean (SD) Median (Q1-Q3) Min-Max N missing						
Type of NVAF	Valid N Persistent Long standing persistent Permanent Paroxysmal N missing						
Modified EHRA scale for AF related symptoms	Valid N 1-none 2a-mild 2b-moderate 3-severe 4-disabling N missing						

Table 10. Procedures and interventions according to current NOAC type

		Dabigatran	Rivaroxaban	Apixaban	Edoxaban	Total	Standardized differences (Pradaxa® vs others)
Cardioversion	Valid N No Yes N missing						
Ablation	Valid N No Yes N missing						
Coronary interventions	Valid N No						

Document: H:\HOR-Europe\2019\2512352 - Study on anticoagulation management - BI\Proyecto\Estadistica\SAP\SAP_REBELD_version1.0_08072020.docx

Author: [REDACTED] Version Number: Version 1.0
Version Date: [08072020]

Template No.: RWI_TP_BIOS0013 Revision 1

Reference: RWI_WI_BIOS0015

Effective Date: 15Jun2018

		Dabigatran	Rivaroxaban	Apixaban	Edoxaban	Total	Standardized differences (Pradaxa® vs others)
	Yes N missing						
Type of coronary interventions	Valid N Percutaneous coronary intervention Coronary artery bypass grafting N missing						
Pacemaker carrier	Valid N No Yes N missing						

Table 11. Clinical risk factors according to current NOAC type

		Dabigatran	Rivaroxaban	Apixaban	Edoxaban	Total	Standardized differences (Pradaxa® vs others)
Heart failure	Valid N No Yes N missing						
NYHA classification	Valid N A - No objective evidence of cardiovascular disease B - Objective evidence of minimal cardiovascular disease C - Objective evidence of moderately severe cardiovascular disease D - Objective evidence of severe cardiovascular disease N missing						
Left ventricular ejection fraction (%)	Valid N Mean (SD) Median (Q1-Q3) Min-Max						

Document: H:\HOR-Europe\2019\2512352 - Study on anticoagulation management - BI\Proyecto\Estadistica\SAP\S
AP_REBELD_version1.0_08072020.docx

Author: [REDACTED] Version Number: Version 1.0
Version Date: [08072020]

Template No.: RWI_TP_BIOS0013 Revision 1

Reference: RWI_WI_BIOS0015

Effective Date: 15Jun2018

		Dabigatran	Rivaroxaban	Apixaban	Edoxaban	Total	Standardized differences (Pradaxa® vs others)
	N missing						
Coronary artery disease	Valid N No Yes N missing						
Sleep apnoea-hypopnoea syndrome	Valid N No Yes N missing						
Hypertension	Valid N No Yes N missing						
Hyperlipidemia	Valid N No Yes N missing						

Table 12. Charlson Comorbidity Index according to current NOAC type

		Dabigatran	Rivaroxaban	Apixaban	Edoxaban	Total	Standardized differences (Pradaxa® vs others)
Myocardial infarction	Valid N No Yes N missing						
Congestive heart failure	Valid N No Yes N missing						
Peripheral vascular disease	Valid N No						

Document: H:\HOR-Europe\2019\2512352 - Study on anticoagulation management - BI\Proyecto\Estadistica\SAP\S AP_REBELD_version1.0_08072020.docx

Author: [REDACTED] Version Number: Version 1.0
Version Date: [08072020]

Template No.: RWI_TP_BIOS0013 Revision 1

Reference: RWI_WI_BIOS0015

Effective Date: 15Jun2018

		Dabigatran	Rivaroxaban	Apixaban	Edoxaban	Total	Standardized differences (Pradaxa® vs others)
	Yes N missing						
Cerebrovascular disease	Valid N No Yes N missing						
Dementia	Valid N No Yes N missing						
COPD	Valid N No Yes N missing						
Connective tissue disease	Valid N No Yes N missing						
Peptic ulcer disease	Valid N No Yes N missing						
Liver disease	Valid N Mild Moderate to severe N missing						
Diabetes mellitus	Valid N Uncomplicated End-organ damage N missing						
Hemiplegia	Valid N No Yes						

Document: H:\HOR-Europe\2019\2512352 - Study on anticoagulation management - BI\Proyecto\Estadística\SAP\S AP_REBELD_version1.0_08072020.docx

Author: [REDACTED]

Version Number:

Version 1.0

Version Date:

[08072020]

Template No.: RWI_TP_BIOS0013 Revision 1

Reference: RWI_WI_BIOS0015

Effective Date: 15Jun2018

		Dabigatran	Rivaroxaban	Apixaban	Edoxaban	Total	Standardized differences (Pradaxa® vs others)
	N missing						
Moderate to severe renal disease	Valid N No Yes N missing						
Solid tumor	Valid N Localized Metastatic N missing						
Leukemia	Valid N No Yes N missing						
Lymphoma	Valid N No Yes N missing						
AIDS	Valid N No Yes N missing						
Age-adjusted Charlson Comorbidity index score	Valid N Mean (SD) Median (Q1-Q3) Min-Max N missing						

Document: H:\HOR-Europe\2019\2512352 - Study on anticoagulation management - BI\Proyecto\Estadistica\SAP\S AP_REBELD_version1.0_08072020.docx

Author:

Version Number:

Version 1.0

Version Date:

[08072020]

Template No.: RWI_TP_BIOS0013 Revision 1

Reference: RWI_WI_BIOS0015

Effective Date: 15Jun2018

